3.6.2.2 Serious Adverse Events

All SAEs will be listed and summarized in a similar manner to TEAEs.

3.6.2.3 Deaths

A listing of deaths will be presented.

3.6.3 Clinical Laboratory Evaluations

Summary statistics for actual values and for changes from baseline will be tabulated for clinical laboratory results by scheduled visit. Subjects with clinical laboratory values outside of the normal reference range at any post-baseline assessment will be summarized. Shifts from baseline clinical laboratory values based upon the normal range and will be tabulated.

Additional blood specimens using the immune response lab kit will be collected for subjects who experience a potential systemic allergic reaction that the Investigator believes is related to ALD403. The immune response lab results will be provided in a listing.

Plots of average clinical laboratory parameters will be presented over time.

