8.2. Exclusion Criteria

A subject who meets any of the following criteria will be excluded from the trial:

1. Receipt of any monoclonal antibody treatment, including ALD403 or any monoclonal antibody targeting the CGRP pathway (within or outside a clinical trial) within 6 months before screening.
2. Confounding and clinically significant pain syndromes (e.g. fibromyalgia, chronic low back pain, complex regional back syndrome, temporomandibular disorders).
3. Psychiatric conditions that are uncontrolled and/or untreated, including conditions that are not controlled for a minimum of 6 months prior to screening. Patients with a lifetime history of psychosis, mania, or dementia are excluded.
4. History or diagnosis of complicated migraine (ICHD-III beta version, 2013), chronic tension-type headache, hypnic headache, cluster headache, hemicrania continua, new daily persistent headache, or sporadic and familial hemiplegic migraine
5. Any use of approved devices, neuromodulation, neurostimulation or injectable therapy (trigger point injections, extracranial nerve blocks, facet joint for headache prophylaxis are prohibited 2 months prior to screening and during screening.
6. Any use of botulinum toxin for migraine or for any other medical/cosmetic reasons requiring injections in the head, face, or neck within 4 months prior to screening and during screening.
7. Any use of monoamine oxidase inhibitors (MAOIs), ketamine, methysergide, methylergonovine, or nimesulide within 3 months prior to screening.
8. Have present or previous malignancies, except:

- Squamous or basal skin cell carcinoma with excision, without evidence of recurrence, or
- Malignancy \geq 10 years since diagnosis/treatment without evidence of recurrence.

9. Subject has known history or evidence of cardiovascular disease, arteriosclerosis, cardiomyopathy, coronary artery disease, serious heart rhythm abnormalities, neurological disease, cerebrovascular disease, diabetes, Raynaud's disease, or life-threatening allergy (e.g., anaphylaxis). If questions arise, the Investigator should contact the Medical Monitor for guidance.

10. Primary hypertension that is uncontrolled or newly diagnosed (systolic BP of >139 mm Hg or diastolic BP of >89 mm Hg) at screening or secondary hypertension. Mild primary hypertension that is well-controlled for ≥ 6 months prior to screening is allowed.

11. Clinically significant abnormal ECG at screening or on Day 0.

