13.4.4.3. Clinical Laboratory Results

Summary statistics for actual values and for changes from baseline will be tabulated for clinical laboratory results by scheduled visit. Subjects with clinical laboratory values outside of the normal reference range at any post-baseline assessment will be summarized. Shifts from baseline clinical laboratory values based upon the normal range will be tabulated. Subjects developing an antibody response will be listed.

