1.3 Sample Size

The planned sample size for this study is 120 treated subjects. It is assumed that over 75% of these subjects will complete the primary treatment phase resulting in at least 90 subjects with one year of safety data collection.

TABLE 1: SCHEDULE OF EVENTS AND ASSESSMENT

Assessments	Screening Day -14 to -11	Day 0	Wk 2 Day 14 ± 3 days	Wk 4 Day 28 ± 3 days	Wk 8 Day 56 ± 3 days	Wk 12 & 24 & 36 Day 84 / 168 / 252 ± 3 days	Wk 48 Day 336 -7/+14 days	Wk 60 & 72 & 84 Day 420 / 504 / 588 ± 7 days	Wk 56 ⁹ or 104 EOT / Early Withdrawal Day 392 or 728 ± 7 days
Informed Consent, Demographics, Medical History, Height	X								
In/Ex Criteria	X	X							
Weight	X	X				X			X
Physical Exam ¹	X	X				X	X ¹¹	X	X
Vital Signs ³	X	X				X	X	X	X
C-SSRS ^{4,1}	X	X	X	X	X	X	X	X	X
PGIC ²				X	X	X	X	X	X
SF-36, HIT-6 ¹	X	X		X		X	X	X	X
EQ-5D-5L ¹²	X	X		X		X	X		X ¹⁰
MBS	X	X		X	X	X	X		X ¹⁰
MIDAS ¹		X				X	X	X	X
AE/ Con Med Review	X	X	X	X	X	X	X	X	X
ALD403 infusion ⁵		X				X	X ¹¹	X	
12-lead ECG ⁷	X	X				X	X	X	X
Hematology, Chemistry ¹	X	X				X	X	X	X
HIV/Hepatitis B and C	X								
Plasma PK ^{6,8}		X	X	X	X	X	X		X
Serum Anti-ALD403 ⁶		X	X	X	X	X	X		X
Urine Drugs of Abuse ¹	X								
Urine Pregnancy Test	X	X		X	X	X	X	X	X

¹ Conduct assessment pre-dose on Day 0 and Week 12, 24, 36, 48, 60, 72, and 84.

² Conduct assessment pre-dose on Week 12, 24, 36, 48, 60, 72, and 84.

³ Conduct assessments pre-dose and up to 2 hours (+ 30 min) post-dose on Day 0 and Week 12, 24, 36, 48, 60, 72, and 84.

⁴ Conduct **C-SSRS Baseline/Screening Version** at screening and **C-SSRS Since Last Visit Version** at remaining visits where C-SSRS required.

⁵ Monitor subjects for at least 2 hours after the end of each dosing to assess for the occurrence of adverse events.

⁶ Collect samples pre-dose on Day 0 and Week 12, 24, 36, 48, and 72. Subjects who test positive for anti-ALD403 antibodies at the last study visit will be asked to provide up to 2 additional blood samples for immunogenicity testing at 3 month intervals for up to 6 months.

⁷ Conduct assessment pre-dose, and within 2 hours (+ 30 min) post dose on Day 0 and Week 12, 24, 36, 48, 60, 72, and 84.

⁸ On Day 0, collect additional sample immediately post-dose (within 15 minutes of end of infusion).

⁹ Subjects who don't received all 4 infusions of ALD403 in the primary treatment phase or don't consent to participate in the secondary treatment phase will have the End of Trial/Early Withdrawal visit at Week 56.

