3 STATISTICAL SUMMARIES

3.1 General Conventions

Unless otherwise stated, summary statistics including the number of subjects (n), mean, standard deviation, median, minimum and maximum will be presented for continuous variables.

Generally, the minimum and maximum values will be presented to the same decimal precision as the raw values, the mean and median values to one more, and the standard deviation, to two more decimal places than the raw values. This decimal place convention may be followed for all data elements. For categorical variables, per category, the absolute counts (n) and percentages (%) of subjects with data, and if appropriate, the number of subjects with missing data, will be presented. Percentages will be presented to one decimal place.

For PK data, the following applies:

Concentration values for free ALD403 will be presented as received from the Bioanalytical Laboratory.

Values for all PK parameters and for mean concentrations will be presented in three or four significant digits, as appropriate, i.e., 3 significant digits for minimum and maximum, 4 significant digits for mean, SD and median; % CV is given to 1 decimal point.

For AEs, medical history and concomitant medications reported on a per-subject basis, the denominator for the percentage calculation will be the number of subjects at risk. A subject will be considered at risk if the subject is in the analysis set and in the subgroup of interest.

Unless otherwise specified all safety as well as demographic and baseline characteristic analyses will be based upon the safety population and all PK analyses will be based upon the PK population.

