3.6.4 Vital Signs, Physical Findings and Other Observations Related to Safety

3.6.4.1 Vital Signs

The observed data at baseline and change from baseline for each measurement day will be summarized with descriptive statistics. A plot of average vital sign parameters will be presented over time.

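### Lab and vital-sign tables have no prespecified size category, so large changes are counted apart from small ones only if reported as adverse events

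*SAP*

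**What the plan says.** SAP 3.6.3 specifies four outputs for hematology and chemistry.

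- By-visit statistics: "Summary statistics for actual values and for changes from baseline will be tabulated for clinical laboratory results by scheduled visit".
- A subject count: "Subjects with clinical laboratory values outside of the normal reference range at any post-baseline assessment will be summarized".
- A shift table: "Shifts from baseline clinical laboratory values based upon the normal range and will be tabulated".
- Plots of averages over time.

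Protocol 13.4.4.3 has the same count and the same shift rule. The only listing named in SAP 3.6.3 is for the immune-response kit.

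For vital signs, SAP 3.6.4.1 plans descriptive statistics at baseline and for change on each measurement day, and adds: "A plot of average vital sign parameters will be presented over time". Under SAP 3.1, "mean, standard deviation, median, minimum and maximum will be presented for continuous variables", so extremes are displayed. Vital signs are taken before and after each infusion (SAP Table 1, footnote 3), but the section does not say which reading is summarized.

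QTcF is treated differently. SAP 3.6.4.3 gives it four absolute categories and two change categories. Liver-test, blood pressure and heart rate terms are adverse events of special interest (SAP 3.6.2.1).

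**The concern.** Long-term safety is the primary objective, and there is no control arm against which to read a background rate of abnormal values. The sponsor has named hepatic and cardiovascular events as topics of interest. Yet the measured data behind those topics are never sorted by size.

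The lab count puts an ALT at 1.1 times the upper limit together with one at 10 times. It does not show whether a transaminase rise and a bilirubin rise occurred in the same person. Vital signs have no subject count at all. By-visit maxima show that an extreme value exists. They do not show how many subjects had one, whether it persisted, or whether two tests rose together.

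The any-visit count also depends on how long a subject is followed. Part of it can rise between the interim analysis and the final analysis, or between subjects who stop at Week 56 and those who reach Week 104, with no change in risk.

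**Working it through.** **The plan's own figure.** 120 × 0.75 = 90 subjects with one year of safety data (SAP 1.3), which reproduces. The documents give no expected rate of abnormal laboratory or vital-sign values.

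**Number of lab visits.** SAP Table 1, footnote 1, which applies to hematology and chemistry, says "Conduct assessment pre-dose on Day 0 and Week 12, 24, 36, 48, 60, 72, and 84". That is 7 post-baseline infusion visits. Adding Week 104 gives 7 + 1 = 8 for subjects in the secondary phase. Subjects who end at Week 56 have Weeks 12, 24, 36, 48 and 56, which is 5 if all are attended. How many subjects enter the secondary phase is not stated.

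**Chance of at least one flag, per analyte.** Two assumptions are not in the documents: 5% of values fall outside the reference range at any visit, and the drug has no effect. If visits within a subject are independent, the chance over k visits is 1 − 0.95^k:

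- k = 1: 5.0%, or 6 of 120 subjects
- k = 5: 1 − 0.95^5 = 22.6%, or about 27 of 120
- k = 8: 1 − 0.95^8 = 33.7%, or about 40 of 120

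If only one direction matters, as for ALT, AST and bilirubin, 2.5% outside is the closer assumption. Then 1 − 0.975^5 = 11.9% and 1 − 0.975^8 = 18.3%.

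**Effect of within-subject correlation (also an assumption).** Independence is the extreme case. Each value was simulated as √ρ × subject effect + √(1 − ρ) × visit noise, with standard normal terms and 400,000 subjects. A value was flagged if it fell outside the central 95%.

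| Correlation ρ | 5 visits | 8 visits | 8 visits, in range at baseline |
|---|---|---|---|
| 0 | 22.6% | 33.7% | 33.6% |
| 0.5 | 18.3% | 25.0% | 23.1% |
| 0.7 | 14.8% | 19.0% | 16.0% |
| 0.8 | 12.7% | 15.7% | 12.2% |
| 0.9 | 10.1% | 11.9% | 7.7% |

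The 8-visit figure therefore runs from about 12% to 34%. At ρ = 0.8, moving from 5 to 8 visits adds 15.7 − 12.7 = 3.0 percentage points. At the same ρ, the share of flagged subjects who were already out of range at baseline is (0.157 − 0.95 × 0.122) / 0.157 = 0.041 / 0.157, or about 26%.

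**What an average can hide (illustration only).** One subject of 120 rising by 40 mmHg moves the mean by 40/120 = 0.33 mmHg. Three such subjects move it by 1.0, and six rising by 30 mmHg move it by 6 × 30/120 = 1.5. The standard error is SD/√120, which is 1.10 at an assumed SD of 12. The documents give none of these rises, counts or SDs, and the conclusion does not rest on them.

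**The case against.** The strongest reply is that the plan does grade and count important changes, in other sections.

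- An Investigator must review every laboratory report and record the clinical significance of each out-of-range value (Protocol 10.2.7.3).
- Findings judged clinically significant are adverse events, graded 1 to 5 (Protocol 11.1.2) and tabulated by severity (SAP 3.6.1).
- Liver-test and blood pressure terms are then summarized again as events of special interest, by maximum severity and relationship (SAP 3.6.2.1).
- Minimum and maximum are shown, and the shift table separates subjects by baseline status.

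All of this stands. A reader might infer that large changes are graded and counted nowhere in the plan; that is wrong. What remains is that this route turns on a judgement made subject by subject at about 20 centers, and an elevation judged not significant never reaches those tables. The grades also describe symptoms, need for intervention and function, not the measured value.

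A reader might also infer that the lab count consists mostly of chance flags. The documents give no reference-range coverage, within-subject correlation or true abnormality rate, so that share cannot be established. Nor do they support the inference that nearly every subject will be flagged. That would require pooling the 29 analytes (19 chemistry and 10 hematology, Protocol 11.1.7) and treating them as independent. The SAP specifies no pooled table, and hemoglobin, hematocrit and red cell count clearly move together.

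Finally, QTcF categories do not oblige the sponsor to do the same elsewhere, and protocol and SAP agree with each other here. Both points are fair; this is a gap, not a contradiction.

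**Conclusion.** The concern holds in a limited form. The lab and vital-sign tables contain no prespecified magnitude category. The only laboratory subject counts use the normal-range cut, and vital signs have no subject count. Large changes are counted apart from small ones only through investigator-reported adverse events.

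This follows from the text and needs no assumption. The chance-accumulation point is secondary. Its size, about 12% to 34% per analyte over 8 visits, rests on assumed 95% ranges, no drug effect and an assumed correlation. At high correlation the growth from 5 to 8 visits is small.

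The planned outputs are not wrong and should stay. They do not describe hepatic and blood pressure safety as well as the collected data allow, in a trial whose primary objective is safety.

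**What to change.** In SAP 3.6.3, keep the shift tables and add treatment-emergent subject counts (criterion not met at baseline) for:

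- ALT and AST at prespecified multiples of ULN, for example >3, >5 and >10;
- total bilirubin >2 × ULN;
- ALT or AST >3 × ULN together with bilirubin >2 × ULN.

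Add a listing of the subjects who meet any of these. The cut-offs are proposed reporting categories. They do not come from the documents and are not treatment rules; the sponsor may choose others if they are fixed in advance. The other 29 − 3 = 26 analytes keep the current outputs.

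In SAP 3.6.4.1, add counts of subjects newly above the limits used for eligibility in Protocol 8.2 ("systolic BP of >139 mm Hg or diastolic BP of >89 mm Hg"), at any visit and at two consecutive visits. Add a prespecified size-of-change category, as is done for QTcF. Report pre-dose and post-dose readings separately.

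The limit alone is not enough. A systolic pressure going from 138 to 140 would be counted, while one going from 105 to 135 would not. An any-visit count against a limit also accumulates with visits, which is why the consecutive-visit count belongs beside it.

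The cost is SAP wording and a few tables. No new data are needed.

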3.6.4 Vital Signs, Physical Findings and Other Observations Related to Safety

3.6.4.1 Vital Signs

The observed data at baseline and change from baseline for each measurement day will be summarized with descriptive statistics. A plot of average vital sign parameters will be presented over time.

3.6.4.2 Physical Exam

Physical exam findings at screening will be documented in medical history. Post baseline physical examination findings, including unscheduled visits, may be reported as adverse events using the protocol adverse event definition.

3.6.4.3 Electrocardiogram Results

The observed data at baseline and change from baseline for each measurement day will be summarized with descriptive statistics.

The overall ECG interpretation based on investigator interpretation will be summarized including post treatment ECGs determined to be abnormal clinically significant.

The absolute QTcF values provided by the core lab will be analyzed as a categorical variable. Each QTcF value in a given patient will be grouped into 4 categories:

- QTcF interval < 450 msec
- QTcF interval 450 - 480 msec
- QTcF interval > 480 - 500 msec
- QTcF interval > 500 msec

The changes in QTcF measures will also be analyzed as categorical variables. The change in QTcF in a given patient will be grouped into 2 categories:

- QTcF interval increases from baseline > 30 msec
- QTcF interval increases from baseline > 60 msec

3.6.5 Immunogenicity Data Analysis

Analyses will be conducted for safety population. Analysis of specific anti-ALD403 antibodies is restricted to subjects who are treated with ALD403.

For subjects with pre-existing antibodies at baseline, the number and percent of subjects who are positive for anti-ALD403 antibody will be summarized. In addition, the number and percent of subjects who develop anti-drug antibodies to ALD403 during the trial will be summarized at each scheduled visit in the same table. Denominators for percentages will be the total number of results available for the specified visit.

All the immunogenicity data will be listed.

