12. Any clinically significant concurrent medical condition or clinically significant laboratory abnormality at screening or on Day 0.

13. Body Mass Index (BMI) ≥ 39 kg/m² at screening.

14. The subject is at risk of self-harm or harm to others in the investigator's opinion, based on clinical interview and responses provided on the Columbia-Suicide Severity Rating Scale (C-SSRS). Subjects must be excluded if they have a lifetime history of a serious suicide attempt or multiple suicide attempts (i.e., actual, interrupted, or aborted attempts), had any suicidal behavior in the past 5 years (i.e., preparatory acts or behavior), or had suicidal ideation of Type 3, 4 or 5 (i.e., suicidal ideation with any method without intent to act or suicidal ideation with intent to act, with or without a plan), in the past 6 months, as measured by the C-SSRS at screening or on Day 0.

15. Any history or evidence of substance abuse or dependence (e.g., alcohol, opiates, amphetamines, and barbiturates) within the past 2 years according to the International Classification of Diseases (ICD) 10: F10-19.

16. Pregnant, breastfeeding, or planning to become pregnant during the trial.

17. Receipt of any experimental, unregistered therapy (within or outside a clinical trial)

within 30 days or 5 plasma half-lives (whichever is longer) before screening.

18. Planned or current participation in any other clinical trial for the duration of this clinical trial, or within 6 months prior to screening. NOTE: Subjects who participated in prior clinical trials of CGRP antagonists, including ALD403-CLIN-005, may be eligible to participate if they
 - had their last dose of study drug more than 6 months prior to screening, AND
 - had no clinically significant adverse events related to study drug during their participation in the prior trial as assessed by the Investigator prior to enrollment.
19. Recent or planned surgery, requiring general anesthesia, within 8 weeks prior to screening and during the duration of this clinical trial.
20. Positive for HIV, hepatitis B surface antigen, or hepatitis C antibody at screening.
21. Any condition that, in the opinion of the investigator, would make the subject unsuitable for the clinical trial.
22. Employees of Alder, the CRO(s), or any clinical trial site involved in this trial and their immediate family members (i.e., parents, spouse, siblings, children).

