2 STATISTICAL METHODS

2.1 *Populations Analyzed*

The analysis populations are defined as the following:

- Safety Population – Includes all subjects who received at least one dose of treatment.
- PK Population - All subjects who have at least one reportable plasma concentration. The PK population will be used for PK analyses.

2.2 *Clinical Trial Endpoints*

The safety, pharmacokinetic and immunogenicity of ALD403 will be assessed using the following endpoints. Greater detail concerning these endpoints can be found in [Section 2.2.1](#).

Safety Endpoints

- Adverse events (AEs) and serious adverse events (SAEs)
- Clinical laboratory assessments
- Vital signs
- Electrocardiograms (ECGs)
- Columbia-Suicide Severity Rating Scale (C-SSRS)

Patient Reported Outcomes:

- Patient Global Impression of Change (PGIC)
- Short-Form Health Survey (SF-36)
- Health-Related Quality of Life (EQ-5D-5L)
- Headache Impact Test (HIT-6)
- Most Bothersome Symptom (MBS)
- The Migraine Disability Assessment (MIDAS)

Pharmacokinetic and Immunogenicity Endpoints

- Free ALD403 plasma concentrations
- Development of specific anti-ALD403 antibodies
- Characterization of specific anti-ALD403 antibodies for neutralizing activity

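### SAP 3.6.5 tabulates antibody development only visit by visit, over all results at the visit, so no planned table gives the treatment-emergent antibody incidence

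*SAP*

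**What the plan says.** Immunogenicity of repeat doses is a secondary objective (Protocol 6.2, SAP 1.1.2). One of the endpoints in SAP 2.2 is "Development of specific anti-ALD403 antibodies".

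SAP 3.6.5 sets the analysis:

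- Population: "Analyses will be conducted for safety population".
- Baseline positives: "For subjects with pre-existing antibodies at baseline, the number and percent of subjects who are positive for anti-ALD403 antibody will be summarized".
- Development, as count and percentage: "subjects who develop anti-drug antibodies to ALD403 during the trial will be summarized at each scheduled visit in the same table".
- Base: "Denominators for percentages will be the total number of results available for the specified visit".

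The only other antibody outputs are listings: all immunogenicity data in SAP 3.6.5, and subjects developing a response in Protocol 13.4.4.3. Neither document defines developing an antibody. In particular, neither says whether a rise in a subject already positive at baseline counts, or whether a subject who has turned positive stays counted at later visits.

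**The concern.** New antibody development is something only a baseline-negative subject can show, and over a trial of up to eight infusions the natural summary is the share of such subjects who ever turn positive. The planned table has no such row. Its visit rows mix onset, loss of response, drop-out and baseline status, and their base changes from visit to visit.

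The next section of the SAP shows that the sponsor knows the alternative. In 3.6.6 a subject counts as a yes on the C-SSRS post-baseline summary if there was a yes at any time after baseline. Antibodies have no equivalent rule.

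At stake is the main number for a stated secondary objective. A report written from the planned table would quote a visit row in its place, or someone would compute an incidence from the listings and choose the definition after seeing the data.

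**Working it through.** **Inputs from the documents**
- 120 treated, over 75% expected to complete the primary phase (SAP 1.3). Check: 120 × 0.75 = 90, which agrees with the plan's figure of at least 90. This is the only planned count that bears on the visit bases.
- Antibody samples on Day 0, at Weeks 2, 4, 8, 12, 24, 36, 48 and 72, and at Week 104 or early termination (SAP 2.2.3).
- Up to two further samples, 3 months apart, only from subjects positive at their last visit (SAP 2.2.3).
- Analysis windows by actual date (SAP Table 2).

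**Assumptions, not in the documents**
- p = 20% of baseline-negative subjects develop antibodies.
- The baseline-positive share b, the onset, the duration and the stopping pattern are varied below.
- A responder is counted at a visit only while positive.

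**Step 1. Base alone.** If baseline positives cannot develop antibodies, the planned percentage is p(1 − b) against p, so the relative shortfall equals b. With 120 subjects and b = 5%, there are 6 baseline-positive and 114 at risk. Then 114 × 0.20 = 22.8, and 22.8/120 = 19.0%. For b = 0, 2, 10 and 20% the result is 20.0, 19.6, 18.0 and 16.0%. At b of 2 to 10% the effect is 0.4 to 2 points.

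**Step 2. Highest visit row against cumulative incidence.** This is a simulation of 120 subjects. Durations are uniform over the range shown. 75% reach Week 48, and 80% of those continue to Week 104 while the rest exit at Week 56. Earlier stoppers leave uniformly over Weeks 2 to 48. Cumulative means ever positive at a sampled visit, divided by baseline-negative subjects. Each range for the highest row runs from b = 10% to b = 2%.

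| Onset (weeks) | Duration (weeks) | Mean highest visit row | Mean cumulative |
|---|---|---|---|
| 2–36 | 8–24 | 10.0–10.7% | about 17% |
| 2–36 | 12–36 | 13.1–14.3% | about 18% |
| 2–36 | 24–60 | 17.3–18.9% | 17.7% |
| 2–12 | 8–24 | 17.7–19.4% | 19.3% |
| 2–84 | 8–24 | about 6% | about 12% |

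Differences of 0.1 to 0.2 points are simulation noise. In the third line the highest row can exceed the cumulative figure for two reasons. The cumulative base keeps subjects who left before they could turn positive, and the highest of nine rows picks up chance variation.

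A second model has exponential durations, onset at Weeks 2 to 36, b = 5%, and 25% stopping after Week 48 regardless of antibody status. It gives 19.1% against 20.1% for persistent antibodies, 13.5% against 18.1% for a mean duration of 48 weeks, and 6.4% against 14.0% for 12 weeks.

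**Step 3. Selective drop-out.** Take persistent antibodies and b = 5%. Responders are 0.95 × 0.20 = 0.19 of all subjects and the others 0.81. If 10% of responders and 35% of the others stop after Week 48, the Week 104 row is (0.19 × 0.90)/(0.19 × 0.90 + 0.81 × 0.65) = 0.171/0.6975 = 24.5%. The cumulative incidence is 20%.

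**Step 4. Positive-only samples.** A Week 56 exit is Day 392, which falls in the Week 60 window (Days 379–462). Three months later is Days 476–483, in the Week 72 window (463–546). Six months later is Days 560–574, in the Week 84 window (546–630). Suppose 90 subjects continue with 20% positive, and 6 of the 30 who stop (20%) give a positive follow-up sample. Week 72 then shows (90 × 0.20 + 6)/(90 + 6) = 24/96 = 25%. Week 84 has no scheduled antibody sample, so a row printed there would show 6/6 = 100%. The SAP does not say whether these samples enter the table.

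**The case against.** The best defence is that this is a descriptive, single-arm objective with no antibody hypothesis or decision rule, that every result is listed, and that with about 120 subjects anyone can count the ever-positive. It is also true that results available at a visit are the natural base for a figure about that visit, and that the text could be read as a running count of subjects who have developed antibodies so far.

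Much of this stands. The visit rows are sound as prevalence, and the consequence is limited. But a listing does not fix numerator and denominator in advance. A running count over a base that changes at each visit would not be a cumulative incidence either.

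Three stronger readings are tempting, and the documents do not support them.

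- *The planned percentage always understates incidence.* Steps 2 to 4 show equality and overstatement under plausible conditions, and with development undefined even the numerator is open.
- *The SAP breaks its own at-risk convention.* SAP 3.1 says of adverse events, medical history and concomitant medications that "the denominator for the percentage calculation will be the number of subjects at risk". Its next sentence defines at risk as belonging to the analysis set and the subgroup. It does not remove subjects who had the condition at baseline, so it offers no contrast.
- *Carry-over from earlier trials will make baseline positives common.* Protocol 8.2, criterion 18, has this note: "Subjects who participated in prior clinical trials of CGRP antagonists, including ALD403-CLIN-005, may be eligible to participate if they" meet conditions that include a last dose more than 6 months before screening. Protocol Table 5.3 shows 531 of 665 subjects randomized to ALD403 in that trial, but this is an allocation ratio. Nothing says how many such subjects enrol here or carry antibodies. Baseline positives are possible, and SAP 3.6.5 provides for them, but no rate can be derived.

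**Conclusion.** The point holds as a gap in the planned output: no treatment-emergent definition, no ever-post-baseline incidence, and visit percentages that do not estimate the development endpoint. It should be fixed, but it does not threaten the trial.

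The direction and size of the discrepancy are not determined by the documents. The planned rows will often be lower when responses are transient and onsets are spread over the trial, in the least favourable case shown by more than half (6.4% against 14.0%). They can be about equal with early onset, and about equal or higher with long persistence, selective loss of antibody-negative subjects, or positive-only samples in the Week 72 and Week 84 windows. The inclusion of baseline positives is the smaller part. All percentages rest on an assumed 20% incidence and on assumed onset, duration, baseline positivity and drop-out.

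**What to change.** In SAP 3.6.5:

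1. Define treatment-emergent antibody as a negative pre-dose Day 0 result followed by any positive post-dose result. State whether boosted responses in baseline-positive subjects are counted and, if so, show them on a separate row.
2. Add a cumulative row for the primary phase and for the whole trial. The base is treated, baseline-negative subjects with at least one post-dose result.
3. Report baseline-positive subjects separately.
4. Keep the visit rows, labelled as prevalence.
5. Exclude from the visit rows the post-study samples drawn only from antibody-positive subjects.

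The cost is SAP wording and one table section, since all the samples are already scheduled. The headline figure may be higher than any single visit row. The cumulative row has a limit that a footnote should state: a subject who leaves early without a positive result counts as not having developed antibodies, so the number followed to each phase end should stand beside it.
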